### **Statistical analysis**

In this study, descriptive statistics were described as frequencies (percentages) for categorical variables or medians (interquartile range [IQR]) for continuous variables. The Mann-Whitney U test for continuous variables and the chi-square test for categorical variables were calculated among the different groups. Sensitivity (SEN), specificity (SPE), and accuracy (ACC) were calculated to evaluate the BE detection performance. A receiver operating characteristic (ROC) curve was plotted, and the area under the ROC curve (AUC) was calculated to assess the overall performance of the VOCs based BE detection model. All statistical analyses were

performed by SAS version 9.4 (SAS Institute Inc., Cary, NC, USA) and the Origin software (version 2018). A p-value<0.05 was considered statistically significant. All tests were two tailed.

## **Study plan**

### **To construct an easy, fast, and non-invasive VOCs-based bronchiectasis detection mode**

This study plans to recruit 200 Bronchiectasis patients diagnosed by HRCT from the Department of Respiratory and Critical Care Medicine of Shanghai Pulmonary Hospital and 200 healthy participants from July,2022 to March,2023.

The exhaled gas of admitted patients was collected on the day of admission, that of outpatients on the day of outpatient service, and that of examinees on the day of physical examination. After the exhaled gas was collected, VOCs were detected by mass spectrometry according to the standard processing flow, and the full spectrum of exhaled VOCs of Bronchiectasis patients and healthy people were analyzed to explore the characteristics of exhaled VOCs of Bronchiectasis patients and healthy people, Analyze the correlation between VOCs and clinical disease severity and prognosis (number of acute exacerbations) characteristics. The data of 400 cases were randomly assigned in a 5:2:3 ratio to the discovery cohort, internal validation, and blinded test cohorts. The discovery and internal validation sets were used for potential VOC biomarkers selection and diagnostic model construction.

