## **Study Design**

### **Study Population:**

The age of all subjects were all older than 18. The study population was recruited from Shanghai pulmonary hospital. Diagnosis of bronchiectasis was performed using chest HRCT scans in suspected patients with coughing and expectoration, or long durations of haemoptysis. Healthy participants were as control. Participants with Interstitial lung disease or Sarcoidosis were as unhealthy control.

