### **Criteria:**

#### **Inclusion Criteria:**

Patients were recruited according to the following inclusion criteria: (1) Age>18 years; (2) the diagnosis of BE was according to European Respiratory Society guidelines for the management of adult bronchiectasis; (3) Willing to join in and sign the informed consent form. Healthy control subjects were recruited according to the following inclusion criteria:(1) Age>18 years; (2) No history of any lung disease (according to pulmonary imaging and physical examinations); (3) Willing to join in and sign the informed consent form.

Unhealthy control subjects were recruited according to the following inclusion criteria: (1) Age>18 years; (2) The diagnosis of ILD was according to HRCT and clinical symptoms by two experts' consensus; (3) The diagnosis of Sarcoidosis (SA) was according to American Thoracic Society Clinical Practice Guideline;(4) Willing to join in and sign the informed consent form.

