### **VOCs analysis:**

To select valuable breathomics features and avoid model over-fitting, a combined feature selection method was executed for breathomics features. Firstly, the breathomics features with no significant differences ( $p > 0.05$ ) between BE and controls were excluded. Then, the VOC ions with low intensity but highly correlated with other selected VOC ions (correlation coefficient  $> 0.9$ ) among all discovery samples were excluded. At last, a random forest (RF) model was constructed on the discovery data set, and the ten most important VOC ions were selected based on the feature coefficient in RF model.

In this study, we constructed BE detection models via six popular ML methods, Random Forests (RF), Logistic regression (LR), Xtreme Gradient Boosting (XGB), K-Nearest Neighbor (KNN), Decision tree (DT) and the soft ensemble algorithm of RF, XGB, and LR, in discovery data set. To evaluate the performance of VOCs based BE detection models, the model detection results were evaluated and compared with the HRCT confirmed diagnosis results in the blinded test set.

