### **To evaluate the VOCs-based bronchiectasis detection mode**

Participants were recruited as mentioned above. The exhaled gas was collected and analysed as previously described. The data of 400 cases were randomly assigned in a 5:2:3 ratio to the discovery cohort, internal validation, and blinded test cohorts. The blinded test set was used for model evaluation.

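### The interstitial lung disease/sarcoidosis control group is defined but has no number, data set or analysis; as written, specificity and AUC are tested only against healthy people

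*Combined protocol and SAP*

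**What the plan says.** The Study Description sets the aim as the accuracy of breathomics for diagnosing bronchiectasis in adults, in an evaluator-blinded case-control design.

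Three groups are defined. Beside BE patients and healthy participants, Study Population states: "Participants with Interstitial lung disease or Sarcoidosis were as unhealthy control". Inclusion Criteria gives this third group its own entry conditions and writes of it in the past tense: "Unhealthy control subjects were recruited according to the following inclusion criteria". Healthy controls must have "No history of any lung disease (according to pulmonary imaging and physical examinations").

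The Study plan names only two groups. Its construction subsection gives as its target "200 Bronchiectasis patients diagnosed by HRCT from the Department of Respiratory and Critical Care Medicine of Shanghai Pulmonary Hospital and 200 healthy participants" and says that "the full spectrum of exhaled VOCs of Bronchiectasis patients and healthy people were analyzed". Both its construction and its evaluation subsections then state: "The data of 400 cases were randomly assigned in a 5:2:3 ratio to the discovery cohort, internal validation, and blinded test cohorts". The evaluation subsection uses the blinded test set to evaluate the model.

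Three places might cover the third group, but none names it:

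- VOCs analysis drops features that show no significant difference "between BE and controls were excluded", without saying which controls.
- Statistical analysis compares the groups without naming them, and lists sensitivity, specificity, accuracy and AUC without naming a control type.
- The evaluation subsection says "Participants were recruited as mentioned above".

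**The concern.** The make-up of the control group decides what specificity, accuracy and AUC mean, and here it cannot be determined from the document.

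If the blinded test set holds only BE patients and people without lung disease, it cannot tell a bronchiectasis signal from a general lung-disease signal. A model that called every ILD/SA patient BE and a model that called none BE would get identical test results. Exclusion Criteria also removes asthma, pneumonia, malignant tumour and COPD, so ILD/SA is the only diseased comparator the document defines, and it is the one left unassigned.

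If ILD/SA participants are instead mixed in with the controls, a single specificity depends on an unstated mix. Leaving the mix open also allows it to be settled after results are seen.

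**Working it through.** **Inputs from the document.** 200 BE and 200 healthy (Study plan, construction subsection); 400 cases split 5:2:3 (both Study plan subsections). The ILD/SA number is not given.

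**Reproducing the plan's figures.**
- Total: 200 + 200 = 400, which matches the stated 400.
- Split: 400 × 5/10 = 200 discovery, 400 × 2/10 = 80 internal validation, 400 × 3/10 = 120 blinded test.
- Places left for ILD/SA: 400 − 200 − 200 = 0, hence 0 of the 120 in the test set.
- Expected test set: 120 × 200/400 = 60 BE and 60 healthy. No stratification is stated; under simple random splitting the healthy count would be about 51 to 69 (95% range, hypergeometric).

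**Three readings.**
1. *Literal.* The 400 is BE plus healthy. The test set holds no ILD/SA, and specificity rests on about 60 healthy people.
2. *ILD/SA counted among the controls.* Then 200 + 200 = 400 cannot stand as written, and a specificity over all controls depends on the mix.
3. *ILD/SA as an extra group outside the 400.* The 400 stands, but the group's size and analysis are not written down.

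**Size under reading 2 (k = number of ILD/SA controls, assumed).** Pooled specificity = specificity in healthy − f × gap, where f is the ILD/SA share of controls and gap is the difference between the two specificities. The test-set mix is taken to equal the overall mix. The last two columns give the fall in pooled specificity for a 10-point gap.

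| k | Added to 200 healthy, f = k/(200 + k) | Within 200 controls, f = k/200 | Fall, added (points) | Fall, within (points) |
|---|---|---|---|---|
| 20 | 0.091 | 0.10 | 0.9 | 1.0 |
| 50 | 0.200 | 0.25 | 2.0 | 2.5 |
| 100 | 0.333 | 0.50 | 3.3 | 5.0 |

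**Precision of a separate ILD/SA specificity (n held out, assumed).** Exact Clopper-Pearson 95% interval; half-width means half the total length, maximised over all possible results x = 0 to n.

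| n | 15 | 20 | 27 | 30 | 47 | 50 | 100 | 104 |
|---|---|---|---|---|---|---|---|---|
| Maximum half-width (points) | 26.1 | 22.8 | 19.7 | 18.7 | 14.9 | 14.5 | 10.2 | 9.97 |

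The smallest n that keeps the maximum within 20, 15 or 10 points is 27, 47 or 104 (n = 26, 46 and 103 give 20.07, 15.1 and 10.01). If the group had already been split 5:2:3, about 30% would be usable: 50 recruited gives 15, 100 gives 30, and 27 usable needs 27/0.3 = 90 recruited.

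**The case against.** The strongest reply is that zero ILD/SA in the test set is only one reading. The document is dated July 2023, after the recruitment window closed in March 2023. It describes unhealthy controls as already recruited, while the 200 + 200 is introduced as a plan, so the Study plan may preserve an older intention beside a later account of conduct. That is possible, although the split of the 400 is also in the past tense, which points the other way. What stands is that the zero follows from the written plan and does not prove what was done. The missing number, data set and analysis remain under every reading.

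A second reply is that BE versus healthy is a legitimate question for an early case-control study, and that no section promises to distinguish BE from ILD/SA. That is fair: the design is limited, not invalid. But the sponsor defined a diseased control group, and must either say what it is for or restrict the conclusion.

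Third, the precision figures are worst cases with assumed sizes. At an observed 90%, half-widths are about 15.2, 9.2 and 6.4 points for n = 20, 50 and 100. Exact intervals are also asymmetric: requiring the longer arm to stay within 20, 15 or 10 points needs 29, 49 or 106. The figures illustrate what a separate estimate would offer; they do not measure the defect.

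**Conclusion.** The concern holds, and the point must be fixed. A defined control group has no stated number, data set or analysis, and the only two groups named in the Study plan use up all 400 cases. Followed literally, the plan tests specificity and AUC against 0 ILD/SA participants, so its results place no limit on specificity against ILD/SA: it could be anywhere from 0 to 100%.

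This rests only on the document's own figures and on taking the Study plan at its word. The shifts in pooled specificity (0.9 to 5.0 points per 10-point gap) and the interval widths rest on assumed group sizes. The actual size and direction of any effect on specificity or AUC cannot be computed from the document.

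**What to change.** **Reconcile the text.** Bring Study Population, Inclusion Criteria, VOCs analysis and both Study plan subsections into line. State how many ILD and how many SA controls there are, which data set they enter, and who counts as a control in feature selection.

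**Evaluate the group separately.** Score the ILD/SA participants not used in discovery or internal validation as their own held-out test group, with one model and one cut-off named and fixed before this group and the blinded set are scored. Report specificity with exact 95% CI, and AUC, separately for BE versus healthy and BE versus ILD/SA. Show any pooled figure beside these, with its mix.

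**If that cannot be done,** limit the conclusion to distinguishing BE from healthy people.

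**Cost.** Wording and one extra set of test-set tables, with no refitting or new recruitment, on three conditions:
- The samples were measured. Exhaled Breath collection covers all participants and says the bags were analysed, which makes this likely, but ILD/SA is not named and unmeasured samples may not be recoverable.
- Some of the group were kept out of discovery and internal validation.
- A final model and cut-off are named. VOCs analysis lists six methods, and no section gives a cut-off.

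If either of the first two fails, the price is the narrower conclusion. The downside is that the estimate against ILD/SA may be less favourable, and it will be imprecise if the group is small.

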### **Clinical Data Collection:**

The clinical information of hospitalized patients was collected through a medical record system and questionnaire survey, including chronic medical history, smoking history, chest HRCT imaging data, annual acute attack frequency, disease severity (BSI score), etc.

The information of health examiners is obtained through a survey questionnaire, including age, chronic medical history, smoking history, family history of tumors, and chest HRCT.

The imaging data were obtained from the Shanghai Shanghai pulmonary hospital. And all clinical data were extracted from the medical system by two individual researchers.

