### **VOCs detection:**

On the HPPI-TOFMS detection platform, soft ionization was achieved by a commercial VUV-Kr lamp with a photon energy of 10.6 eV to predominantly produce radical cations ( $M^+$ ) which are formed as  $M + h\nu \rightarrow M^+ + e$ , which can ionize most VOCs in the breath sample. Meanwhile, some protonated ions are also produced. The VOCs with mass-charge ratio( $m/z$ ) in the range of [20, 320] were detected on HPPI-TOFMS. In this study, the area of the strongest peak in the range of  $[x-0.5, x+0.5]$  was calculated, normalized, and regarded as the feature of VOC with  $m/z$  of  $x$ . Thus, three hundred kinds of VOC ions features were extracted via breath detection in HPPI-TOFMS.

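### The VOC correlations with severity and exacerbations have no stated multiplicity control, and the data described support an association, not a prognostic claim

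*Combined protocol and SAP*

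**What the plan says.** The first part of the Study plan section of the combined protocol and SAP contains the only mention of this analysis: "Analyze the correlation between VOCs and clinical disease severity and prognosis (number of acute exacerbations) characteristics". The same sentence states that "the full spectrum of exhaled VOCs of Bronchiectasis patients and healthy people were analyzed".

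The other relevant text is spread over four sections:

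- **VOCs detection:** "three hundred kinds of VOC ions features were extracted".
- **VOCs analysis:** for the detection model, ions are screened on the difference between bronchiectasis and controls and thinned for high mutual correlation. Then "the ten most important VOC ions were selected" by random forest importance. This set is not said to be the one used for the severity and exacerbation correlations.
- **Statistical analysis:** "A p-value<0.05 was considered statistically significant", with two-tailed tests. The methods named are Mann-Whitney, chi-square, sensitivity, specificity, accuracy and ROC/AUC. No correlation coefficient and no adjustment for multiple testing is named.
- **Clinical Data Collection:** "The clinical information of hospitalized patients was collected through a medical record system and questionnaire survey", and the items listed include "annual acute attack frequency, disease severity (BSI score), etc". The list for health examinees contains neither severity nor attack frequency.

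Breath is collected on the day a patient is admitted, and "that of outpatients on the day of outpatient service". No follow-up visit, follow-up period or later count of exacerbations is described anywhere.

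**The concern.** There are two gaps in the same clause.

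The first is the error rate. Many ions may be correlated with at least two clinical variables, and the only threshold in the plan is a per-test 0.05. A list of ions reported as related to severity or exacerbations could then consist partly or largely of chance findings, and a reader would have no stated rate by which to discount it.

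The second is the label. A prognostic statement needs an outcome that comes after the measurement. The exacerbation variable described is an annual frequency whose time window is not given, set against one breath collection visit. Calling it prognosis invites readers to take a cross-sectional association as prediction.

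What is at stake is the reading of a secondary result, not the diagnostic accuracy result.

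**Working it through.** The plan states no power, error rate or sample size for these correlations, so there is no figure to reproduce.

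**Inputs from the document.** 300 ion features (VOCs detection); ten selected ions (VOCs analysis); two-tailed 0.05 (Statistical analysis); 200 bronchiectasis patients and a 5:2:3 split (Study plan).

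**Assumed inputs.**

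- The 0.05 rule applies to the correlations.
- There are two outcomes, the BSI score and the exacerbation count. The text does not fix this number: the data list is open-ended and the Study plan speaks of characteristics.
- The number of patients is 200 (all), 140 (discovery plus internal validation, 7/10 of 200) or 100 (discovery only, 5/10 of 200), if the split is balanced by group. It could differ again, because these clinical data are described for hospitalised patients while outpatients are also sampled.

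**Step 1. Expected false positives if no ion is related** (number of tests × 0.05; independence is not needed).

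- 300 ions: 300 × 0.05 = 15 per outcome; 600 × 0.05 = 30 for two.
- Ten ions: 10 × 0.05 = 0.5 per outcome; 20 × 0.05 = 1 for two.

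**Step 2. Chance of at least one false positive, ten ions and two outcomes.** With independent tests, 1 − 0.95^20 = 0.64. With equally correlated normal test statistics it is 0.42 at a correlation of 0.5 and 0.22 at 0.8 (assumed correlations). The chance of none is therefore 36% to 78%.

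**Step 3. Share of a declared list that is false,** if k of m ions are truly related and each is found with 80% power (both assumed): (m − k) × 0.05 / [(m − k) × 0.05 + 0.8k].

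- m = 300: k = 10 gives 14.5/22.5 = 64%; k = 30 gives 13.5/37.5 = 36%; k = 60 gives 12/60 = 20%.
- m = 10: k = 1 gives 0.45/1.25 = 36%; k = 3 gives 0.35/2.75 = 13%.

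**Step 4. What control would cost.** Under Benjamini-Hochberg at 5%, a single isolated ion must reach 0.05 divided by the number of tests. The critical absolute correlation is t/√(n − 2 + t²). The correlation detectable with 80% power is tanh[(z for the two-sided level + z for 80% power)/√(n − 3)].

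| Tests | Level for an isolated ion | Critical absolute r at n = 200 / 140 / 100 | r detectable with 80% power at n = 200 / 140 / 100 |
|---|---|---|---|
| Unadjusted | 0.05 | 0.139 / 0.166 / 0.197 | 0.197 / 0.235 / 0.277 |
| 20 | 0.0025 | 0.213 / 0.254 / 0.299 | 0.269 / 0.319 / 0.373 |
| 600 | 0.0000833 | 0.275 / 0.326 / 0.383 | 0.328 / 0.387 / 0.450 |

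The bar is lower when many ions are related. In a simulation of 1,000 runs with 600 independent tests, 60 of them truly at r = 0.25 (assumed), Benjamini-Hochberg power was 0.76 against 0.95 unadjusted at n = 200, and 0.25 against 0.71 at n = 100. False positives averaged 2.2 against 27.0 at n = 200, and 0.8 against 26.9 at n = 100.

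**Step 5. Timing.** Breath collection is tied to one visit. The exacerbation data described are an annual frequency from records and a questionnaire. That this is the count meant in the Study plan is itself an assumption, but no other exacerbation variable appears. Nothing places the count after the breath sample.

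**The case against.** The strongest reply is that the clause says only that correlations will be analysed. It promises no list of significant ions, no endpoint and no prediction. The study's aim is diagnostic accuracy, the same sentence speaks of exploring VOC characteristics, and prognosis is glossed in brackets as an exacerbation count, so a reader can see what is measured. Much of this stands. The analysis is secondary, and the use of p<0.05 for it is inferred, although no other rule exists. The correlations are not themselves labelled exploratory, however, and the 0.05 threshold is stated without qualification.

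Some stronger readings are tempting, and the document does not support them:

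- *The list is certain to contain false positives.* With ten ions the chance of any is 22% to 64% when no ion is related. Even on the full spectrum, 15 per outcome is an expectation under the null; ions are likely to be correlated with one another, so the actual count could vary widely around it.
- *The exacerbation count is retrospective.* The time window is not stated. What can be said is that no follow-up is described.
- *The selection of ten ions already controls the error.* It selects ions that separate patients from controls, and sets no error rate for correlations with severity.

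It is also fair to object that a family pooled over both outcomes and a Spearman coefficient are partly preferences.

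**Conclusion.** The point holds in a limited form. The plan states no error-rate control for these correlations. If its general rule is the one used, the expected number of false positives per outcome when no ion is related runs from about 0.5 to about 15, depending on an ion set the plan does not name. The share of a declared list that would be false cannot be fixed, because the document gives no indication of how many ions are truly related; the shares in the working are illustrations. Totals over two outcomes rest on the assumption that there are two.

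On timing, the data as described support a cross-sectional association with recorded exacerbation frequency and do not support a prognostic claim.

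A reader might infer that the breath test's accuracy results are in doubt for this reason. They are not: AUC, sensitivity and specificity do not depend on these correlations. The change should be made, but it is not critical to the study's main conclusion.

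**What to change.** 1. Control the false discovery rate, for example by Benjamini-Hochberg at 5%, over the ion-by-outcome correlations actually run. State which ions, outcomes and patients these are.
2. Name the coefficient. A rank correlation such as Spearman would fit the medians and Mann-Whitney tests already planned, but it is a choice and not a requirement; it adds about 0.01 to the detectable correlations.
3. Report each coefficient with its 95% interval and number of patients, and label the analysis exploratory.
4. State whether the exacerbation count precedes or follows breath sampling. Unless it can be shown to follow sampling over a stated window, replace *prognosis* with *recorded annual exacerbation frequency*.

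**Cost.** No new breath samples are needed. The document is dated July 2023, after the planned end of recruitment in March 2023, so any correlations already run should be reported with adjusted p-values. Rewording cannot supply a time window that the records or questionnaire did not fix. Fewer ions will be declared significant, and the loss of power is material if only about 100 patients are used.
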